12.3. Pharmacokinetic Evaluations

12.3.1. Sample Collection Volumes and Timepoints

PK sampling has been discontinued in Amendment 6. The SSC has eliminated dose escalation in Amendment 5. Most recent PK data shows that only 5% of the active ingredients for a given dose are present in the blood and the concentrations show a meaningful dose response. As a result, the SSC determined that PK sample collection is no longer necessary in Amendment 6. A final PK analysis section will be included in the final clinical study report.

13. ADVERSE EVENT REPORTING

Clinical adverse events occurring after signing informed consent/HIPAA authorization, but before study drug administration are to be recorded on the Medical History/Current Medical Conditions CRF.

13.1. Definitions

An adverse event is any undesirable sign, symptom, clinically significant laboratory abnormality, or medical condition occurring after starting study treatment, even if the event is not considered to be study drug-related. Each adverse event is to be reported on an Adverse Event CRF page. Adverse events are graded using the Cancer Therapy Evaluation Program (CTEP) CTCAE, Version 4.03. If CTCAE grading does not exist for an adverse event, the severity of mild (1), moderate (2), severe (3), life-threatening (4), and death related to an adverse event (5) will be used. Information about all adverse events, whether volunteered by the subject, discovered by Investigator questioning, or detected through physical examination, laboratory testing, or other means, will be collected, and recorded on the Adverse Event CRF page and followed as appropriate. Adverse event monitoring should be continued until adverse event resolution/stabilization (whichever is later).

Medical conditions/diseases present before the injection of study drug are only considered adverse events if they worsen after receiving any study drug. Clinical events occurring before the administration of study drug but after signing the ICF and providing HIPAA authorization are to be recorded on the Medical History/Current Medical Conditions CRF page. All laboratory values are to be reviewed by the Investigator and abnormal values will be graded according to CTCAE Version 4.03 and reported in the study report.

A laboratory abnormality is considered an adverse event if it results in:

- discontinuation from study drug,
- necessitates therapeutic medical intervention,
- if the Investigator assesses the abnormality as an adverse event, or
- any laboratory test that is clinically significant or meets the definition of a SAE

It is expected that wherever possible, the clinical, rather than the laboratory term would be used by the reporting investigator (e.g., anemia versus low hemoglobin value). These adverse events will be recorded on the Adverse Events CRF page and will include all signs, symptoms, or diagnosis associated with them.

As far as possible, each adverse event will also be described by:

1. Description
2. Duration (start and end dates)
3. CTCAE Grade 1 through 5 or severity if CTCAE is not available
4. Relationship to the study drug - related or not related
5. Relationship to the dosing procedure – related or not related
6. Action(s) taken with study drug
7. Whether event was serious
8. Whether event is ongoing (i.e., not resolved).

Relationship to Study Drug

The relationship of each adverse event to study drug will be defined as “not related” or “related”. The Investigator is responsible for determining the study drug relationship for each adverse event that occurs during the study. Assessments are to be recorded on the appropriate CRF page.

Not related

The temporal relationship of the clinical event to study drug administration makes a causal relationship unlikely, or other drugs, therapeutic interventions or underlying conditions provide a sufficient explanation for the observed event.

Related

The temporal relationship of the clinical event to study drug administration makes a causal relationship possible, and other drugs, therapeutic interventions or underlying conditions do not provide a sufficient explanation for the observed event.

Action(s) Taken

The actions taken with study drug in response to an adverse event are described. One or more of these are to be selected:

- No action taken
- Study drug permanently discontinued due to this adverse event
- Study drug temporarily interrupted
- Study drug dosage adjusted

13.1.1. Safety Reporting for Adverse Events

All adverse events or other clinically relevant adverse events occurring up to 28 days after administration of the last dose of study drug will be collected for subjects continuing in the study.

For subjects who discontinue from the study within 28 days after the administration of the last dose of study drug:

- Study drug-related adverse event information will be collected and should be followed to resolution/stabilization
- Adverse events that lead to the discontinuation should be followed to resolution/stabilization
- A telephone contact for the safety update would be acceptable if the subject cannot manage an office visit
- Only study drug-related serious or other clinically significant adverse events will be collected for all subjects > 28 days after the administration of the last dose of study drug.

A *nonserious adverse event* is an AE not classified as serious.

The collection of nonserious AE information should begin at initiation of study drug (day 0) and should conclude 28 days after last dose of study drug. Nonserious AEs should be followed to resolution or stabilization, or reported as SAEs if they become serious (see Section 13.2). Follow-up is also required for nonserious AEs that cause interruption or discontinuation of study drug, or those that are present at the end of study treatment as appropriate. All identified nonserious AEs must be recorded and described on the nonserious AE page of the CRF.

13.2. Serious Adverse Events

A serious adverse event is defined in general as an untoward (unfavorable) adverse event which:

1. is fatal or life-threatening (defined as an event in which the subject was at risk of death at the time of the event; it does not refer to an event which hypothetically might have caused death if it were more severe);
2. requires or prolongs hospitalization;
3. is significantly or permanently disabling or incapacitating;
4. constitutes a congenital anomaly or a birth defect; or
5. may jeopardize the subject and may require medical or surgical intervention to prevent one of the outcomes listed above. (Examples of such events include, but are not limited to, intensive treatment in an emergency room or at home for allergic bronchospasm; blood dyscrasias or convulsions that do not result in hospitalization.)

Suspected transmission of an infectious agent (e.g. any organism, virus or infectious particle, pathogenic or non-pathogenic) via the study drug is a SAE.

Although pregnancy, overdose (greater than 50% more than the intended dose) and cancer are not always serious by regulatory definition, these events must be reported to the Sponsor within 24 hours (See Section 13.5 for reporting pregnancies).

NOTE: Progressive disease is not considered a SAE.

The following hospitalizations are not considered SAEs in Sponsor clinical studies:

- a visit to the emergency room or other hospital department < 24 hours, that does not result in admission (unless considered "important medical event" or event life threatening)
- elective surgery, planned prior to signing consent
- admissions as per protocol for a planned medical/surgical procedure
- routine health assessment requiring admission for baseline/trending of health status (e.g. routine colonoscopy)
- medical/surgical admission for purpose other than remedying ill health state and was planned prior to entry into the study. Appropriate documentation is required in these cases.

- admission encountered for another life circumstance that carries no bearing on health status and requires no medical/surgical intervention (e.g., lack of housing, economic inadequacy, care-giver respite, family circumstances, administrative).
- Hospitalizations occurring under the following circumstances are not considered serious adverse events: admission to a hospice for respite care; hospitalizations planned before entry into the clinical study; hospitalization for elective treatment of a condition unrelated to the studied indication or its treatment; hospitalization on an emergency, outpatient basis that does not result in admission (unless fulfilling the criteria above); hospitalization as part of the normal treatment or monitoring of the studied indication; or hospitalization to facilitate the work up of a Grade 1 adverse event, including overnight hospitalization following study drug administration for nonmedical reasons.

13.3. Rapid Notification of Serious Adverse Events

13.3.1. Reporting Responsibility

Any serious adverse event occurring in a subject after he/she has provided informed consent and HIPAA authorization, and while receiving study treatment; or during the 28 days following study drug administration; or within 28 days of the last visit for screen failures must be reported.

The timeframe for reporting after discontinuation of study drug may be extended if there is a strong suspicion that the study drug has not yet been eliminated or the pharmacodynamic effects of the study drug persist beyond 28 days. All serious adverse events must also be reported for the timeframe in which the study drug interferes with the standard medical treatment given to a subject.

The investigator should collect any SAE occurring after these time periods that is believed to be related to study drug or protocol-specified procedure. A SAE report should be completed for any event where doubt exists regarding its status of seriousness.

If the investigator believes that a SAE is not related to study drug, but is potentially related to the conditions of the study (such as withdrawal of previous therapy, or a complication of a study procedure), the relationship should be specified in the narrative section of the SAE Report Form.

Each serious adverse event must be reported by the Investigator to Propharma (SAE Reporting [contact]), or designee, within 24 hours of learning of its occurrence, even if it is not felt to be related to study drug. Serious adverse events occurring after 28 days from the last dose of INT230-6 must be reported if deemed related to study drug. The report must include the adverse event term, subject identifier, attribution, description, concomitant medication used to treat the adverse event, and any other relevant information. Follow-up information about a previously reported serious adverse event must also be reported to Sponsor within 24 hours of receiving the information. Sponsor, or its designee, may contact the Investigator to obtain further information about a reported serious adverse event. If warranted, an Investigator Alert may be issued to inform all Investigators involved in any study with the same study drug that a serious adverse event has been reported.

13.3.2. Reporting Procedures

The Investigator must complete the Serious Adverse Event Report Form in English, assess the causal relationship to study drug, and send the completed form to the **SAE Reporting [contact]-**

Protocol IT-01 Version Amendment 6

[name]) within 24 hours, to Sponsor or its designee. The study monitor will review the Serious Adverse Event Report Form and the supporting source documents during monitoring visits.

Follow-up information should be sent to the same SAE Reporting Fax Number that received the original Serious Adverse Event Form, within 24 hours of the time the information is known. Either a new Serious Adverse Event Report Form is faxed (indicating that the information is a follow-up), or the original form may be re-faxed (with the new information highlighted and a new date provided). The follow-up report should describe whether the serious adverse event has resolved or is continuing, if and how it was treated, and whether the subject continued or permanently discontinued study participation. The form(s) and FAX confirmation sheet(s) must be retained in the investigational site study file.

The Investigator is responsible for informing the Institutional Review Board/Independent Ethics Committee/Review Ethics Board (IRB/IEC/REB) of the serious adverse event and providing them with all relevant initial and follow-up information about the event. Sponsor or designee will communicate serious adverse events to the study sites as required by regulatory authorities.

SAEs must be recorded on the Sponsor SAE Report Form; pregnancies on a Sponsor Pregnancy Surveillance Form. These original Sponsor Forms are to remain on site. SAEs, whether related or not related to study drug, and pregnancies must be reported to Sponsor within 24 hours via confirmed facsimile (fax) transmission, or scanned and reported via electronic mail to:

SAE Email Address: [contact]

SAE [contact]

If only limited information is initially available, follow-up reports are required. (Note: Follow-up SAE reports should include the same investigator term(s) initially reported.) If an ongoing SAE changes in its intensity or relationship to study drug or if new information becomes available, a follow-up SAE report should be sent within 24 hours to the Sponsor using the same procedure used for transmitting the initial SAE report.

All SAEs should be followed to resolution or stabilization.

13.4. Overdose

An overdose is defined as the accidental or intentional injection of any excessive dose of INT230-6 (for this study it is defined as $\geq 50\%$ of the intended dose).

Any overdose must be recorded in the trial medication section of the CRF. In the event of overdose of INT230-6, subjects should receive appropriate advice and supportive medical care by the investigator or his/her designee and be followed-up accordingly. For monitoring purposes, any case of overdose – whether or not associated with an AE (serious or non-serious) – must be reported to the Sponsor in an expedited manner.

13.5. Pregnancy

Pregnancy testing must be performed in all women of childbearing potential throughout the study as specified in the Time and Event Schedule table, and the results of all pregnancy tests (positive or negative)

Protocol IT-01 Version Amendment 6

are to be recorded on the CRF. All women of childbearing potential must have a negative pregnancy test before each INT230-6 injection. If the pregnancy test is positive, the subject must not receive INT230-6 and must not continue in the study. The subject will be followed to determine the outcome of the pregnancy.

Females of non-childbearing potential are defined as females with functioning ovaries with a documented history of tubal ligation or hysterectomy or females who are post-menopausal, as defined by 12 months of spontaneous amenorrhea with an appropriate clinical profile, e.g., age appropriate, > 45 years, in the absence of hormone replacement therapy. In questionable cases, a blood sample for follicle stimulating hormone and estradiol will be obtained to confirm childbearing potential.

In addition, all women of childbearing potential should be instructed to contact the Investigator immediately if they suspect they might be pregnant (e.g., missed or late menstrual period) at any time during the study Treatment Period part of the study or during the 60-day period following their last dose of study drug.

Male subjects should contact the Investigator immediately if they suspect they may have fathered a child during the study Treatment Period part of the study or during the 180-day period following their last dose of study drug. When possible, partner's pregnancies should be followed (to term) to determine the outcome.

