10. Prior systemic radiation therapy (either IV, intrahepatic or oral) completed at least 4 weeks prior to study drug administration; **(for ipilimumab combination please see supplement FEC exclusion criteria).**
11. Prior focal radiotherapy completed at least 2 weeks prior to study drug administration.
12. Prior major treatment-related surgery completed at least 4 weeks prior to study drug administration.
13. No prior primary or metastatic brain or meningeal tumors unless clinically and radiographically stable as well as off steroid therapy for at least 2 months.
14. Life expectancy ≥ 8 weeks; **(for ipilimumab combination please see supplement FEC inclusion criteria).**
15. A female participant is eligible to participate if she is not pregnant, not breastfeeding, and at least one of the following conditions applies:
 - a. Not a woman of childbearing potential (WOCBP)
 - b. A WOCBP subject who may become pregnant or who are sexually active with a partner and who could become pregnant agrees to use an effective form of barrier contraception during the study and for at least 180 days in monotherapy; **(for pembrolizumab and ipilimumab combinations please see supplements DEC/DEC2 and FEC for pregnancy criteria).** (Male subjects must agree to use contraception and refrain from sperm donation during the study for 180 days after administration of study drug.)
16. Have adequate organ function as defined by the below screening laboratory values that must meet the following criteria:
 - a. WBC $\geq 2000/\mu\text{L}$ ($\geq 2 \times 10^9/\text{L}$).
 - b. Neutrophils $\geq 1000/\mu\text{L}$ ($\geq 1 \times 10^9/\text{L}$); **(for pembrolizumab and ipilimumab combinations please see supplements DEC/DEC2 and FEC for neutrophil criteria).**
 - c. **For subjects with planned superficial only injections:** PT, PTT/aPTT, and INR $\leq 1.5 \times \text{ULN}$, Platelets $\geq 70 \times 10^3/\mu\text{L}$ ($\geq 70 \times 10^9/\text{L}$), Hemoglobin $\geq 8 \text{ g/dL}$
 - d. Creatinine within the institution's laboratory upper limit of normal or calculated creatinine clearance $> 50 \text{ ml/min}$; **(for pembrolizumab combination please see supplements DEC/DEC2 for creatine criteria).**
 - e. ALT (SGOT)/AST (SGPT) $\leq 2.5 \times \text{ULN}$ without, and $\leq 5 \times \text{ULN}$ with hepatic metastases.

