Targeted Physical Examination ²		X	X	X	X	X	X	X	X	X	X	X			X
Weight ³	X					X				X					X
Vital Signs ⁴	X	X	X	X	X	X	X	X	X	X	X	X			X
Assessment of Signs and Symptoms	X	X	X	X	X	X	X	X	X	X	X	X			X
Adverse Events Assessment	X	X	X	X	X	X	X	X	X	X	X	X			X
Laboratory Tests ⁵	X	X	X	X	X	X	X	X	X	X	X	X			X
Pregnancy test ⁶	X			X		X		X		X					X
ECOG Performance status ⁷	X	X	X	X	X	X	X	X	X	X	X	X			X
US/CT of injected tumor ⁸	X			X		X		X		X					X
Tumor imaging (CT/MRI chest/abdomen/pelvis) ^{9, 10, 11}	X ¹¹														X ^{9, 10}
Additional blood or radiographic measures clinically indicated ¹²	X					X				X					X
Clinical Drug Supplies	X			X		X		X		X					X
Dispense Study Treatment	X			X		X		X		X					X

Table 12: Schedule of events every 14 day dosing (monotherapy E cohorts)

Procedure	Cycle1 (+/- 1 Day)					Cycle 2 (+/- 1 Day)				Cycle 3 (+/- 1 Day)			Maintenance
	Day 0 dosing	Day 1	Day 7	Day 14	Day 21	Day 0 dosing	Day 7	Day 14	Day 21	Day 0	Day 7	Day 14	
Vital Status													X
On study biopsy ¹³	X					X							
Concomitant medications	X	X	X	X	X	X	X	X	X	X	X	X	X
Anti-Cancer medications													X
ECG ¹⁴ if medically indicated	X												

Footnotes are shown after Table 13

Table 13: Schedule Follow up Period				
	End of Treatment ¹	Long Term Follow Up (every 9 weeks from last cycle)	End of Follow Up (Subject has PD and moves to Survival FU)	Survival Follow Up
Targeted PE ²	X	X	X	
Weight ³				
Vital signs ⁴	X	X	X	
	X	X		
Assessment of SXS				
Adverse Events	X	X		
Laboratory Tests ⁵	X			
Pregnancy test ⁶	X			
ECOG ⁷	X			
Tumor imaging ^{9 10}		X	X	
Additional blood or radiologic assessment ¹¹ , as applicable ¹²	X	X		
Vital status				X
Con meds	X	X	X	
Report any subsequent anti-cancer therapy			X	X

1 EOT visit to be completed when a subject withdraws from treatment and is not going to proceed to additional cycles of treatment.

2 Physical examination to be conducted and any new or worsening signs and symptoms are to be recorded.

3 Height/weight to be taken at baseline must be collected at these times as well, and then only repeat weights at the start of each cycle.

4 O₂ saturation and resting blood pressure. On the day of each injection, vital signs will be obtained before injection and then 15, 30 and 60 minutes post injection. In addition, for cycle 1, vital signs will be collected at 180 and 360 minutes, including O₂ saturation, and resting blood pressure.

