5 CBC with Differential, Chemistry and Urinalysis as outlined in Section 12.1.2. Grade 3 laboratory abnormality should be assessed for potential risk to continued dosing. In the event of uncertainty, the Sponsor medical monitor should be contacted. ≥ Grade 3 laboratory abnormality should be assessed for potential risk to continued dosing.

6 Serum or urine pregnancy testing must be performed for woman of childbearing potential and found to be negative before dosing.

7 ECOG performance status to be assessed before each injection.

8 Measurements used to guide placement of the needle for injection.

9 The same technique (CT/MRI or PET/CT) used at screening should be used throughout the study.

10 Investigators will assess tumor response using CT/MRI or PET/CT measurements. Assessments should occur 12 weeks +/- 10 days from the first dose (Cycle 1, D0) and then every 9 weeks +/- 10 days for every image thereafter.

11 Tumor imaging only needs to be collected if it has not occurred within the last 29 days.

12 Serum based disease markers if appropriate will be collected at the same timepoints as tumor imaging. Other imaging to be collected as clinically indicated (i.e., brain scans, etc.).

13 Subjects must consent to fresh repeat biopsies of tumors taken prior to dosing on days 0 and 28 (day 0 in cycle 2) during the course of the study at injection sites are mandatory unless cleared by the Sponsor medical monitor. Additionally, 1 biopsy of an untreated bystander tumor that is readily accessible without the need for general anesthesia should be taken by the attending physician if possible; however, if risk too high such bystander biopsy should not be taken. **The post-dose biopsy sample must be taken from the same lesion(s) that were collected at pre-dose (C1D0). If there is an issue that precludes the ability to biopsy the same pre-dose lesion at the later timepoint (C2D0), please inform the Medical Monitor and attempt to biopsy from the pre-dose lesions during a subsequent visit.**

14 Baseline ECG to be done and repeated only if medically indicated throughout the study.

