12.1.4. Follow-up Period

Follow-up visits will be conducted after completion of the Treatment Period (induction and maintenance for those cohorts with maintenance treatment) or as indicated in Section 5.4. Patients who receive all 5 treatment doses or discontinue treatment for any reason except Disease Progression, or Withdrawal of consent should enter Long Term Follow up Period. These patients are to be evaluated every 9 weeks including scans until disease progression or they receive an intervening anti-cancer medication. After documented disease progression or receipt of an intervening anti-cancer medication, patients will enter Survival Follow up. During this time, patients will be contacted every 3 months for patient status (phone call or clinic visit). For subjects who discontinue treatment due to progression, follow-up should be completed approximately every 3 months as noted below (survival follow up). Completion of subsequent follow-up visits will depend on the status of the subject at the end of treatment. All subjects will be followed from the last visit until progression, initiation of a new therapy, or the duration of the study (4 years), whichever occurs first.

Following completion of the treatment and follow-up periods, all subjects will be followed for survival after completion of treatment phases and through the follow up period of the protocol. Subjects will have their survival status assessed approximately every 3 months by either a telephone, in-person contact, or chart review until study completion or termination by the Sponsor. No other data (e.g., subsequent therapies, performance status etc.) beyond survival will be collected during these calls/visits.

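### Women in monotherapy must use contraception for at least 180 days but are told to report a suspected pregnancy only up to 60 days after the last dose, while men have 180 days for both; pregnancies in days 61-180 may be missed.

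*Protocol*

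**What the plan says.** Protocol Section 6.1, inclusion criterion 15b (repeated in the synopsis), requires women of childbearing potential to use an "effective form of barrier contraception during the study and for at least 180 days in monotherapy". It does not say when the 180 days begin, and it refers to the supplements for the combination cohorts. The same item covers men: "Male subjects must agree to use contraception and refrain from sperm donation during the study for 180 days after administration of study drug".

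Protocol Section 13.5 sets out when participants should tell the investigator about a suspected pregnancy. For women this is during the Treatment Period "or during the 60-day period following their last dose of study drug". For men who may have fathered a child it is during the Treatment Period or "during the 180-day period following their last dose of study drug".

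The site's own duty has no such limit. Under Protocol Section 13.3.2, "pregnancies must be reported to Sponsor within 24 hours". Section 13.5.1 asks that pregnancies be followed to their outcome.

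**The concern.** For men, the contraception period and the notification period are the same length. For women in monotherapy they differ, and the protocol gives no reason. INT230-6 contains cisplatin and vinblastine, and the protocol itself treats the period to day 180 as needing contraception. A contraceptive failure late in that period is the kind of case the outcome tracking in Section 13.5.1 is there to record, yet a woman who follows Section 13.5 literally has no reason to call the site after day 60.

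What is at stake is safety information: pregnancy outcomes may be captured less completely for treated women than for the partners of treated men. The SAP's only use of pregnancy data is a listing of test results (SAP Section 10.2), so no estimate depends on this.

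**Working it through.** There is no planned figure to reproduce. The check compares the stated periods and then asks whether anything else covers the difference.

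**Inputs**

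| Duty | Women, monotherapy | Men | Source |
|---|---|---|---|
| Contraception | at least 180 days | 180 days | Protocol 6.1, item 15b |
| Notify a suspected pregnancy | 60 days after last dose | 180 days after last dose | Protocol 13.5 |

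**Uncovered period** = contraception period - notification period, taking the 180 days from the last dose (an assumption for women):

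- Women: 180 - 60 = 120 days (days 61-180).
- Men: 180 - 180 = 0 days.
- If the women's 180 days start instead at the end of study participation, the uncovered period exceeds 120 days.

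**Does anything else cover days 61-180?**

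1. *Pregnancy testing.* Table 13 marks a test at End of Treatment only. The table did not extract cleanly, but footnote 6 points the same way by tying testing to dosing: "Serum or urine pregnancy testing must be performed for woman of childbearing potential and found to be negative before dosing".
2. *Long Term Follow-up.* Visits are every 9 weeks, or 63 days. Counted from the last dose they fall on days 63, 126 and 189, so 2 lie in days 61-180. Counted from the end of a 28-day last cycle they fall on days 91, 154 and 217, again 2. The +/-10 day scan window could move the last-dose count either way: the first visit could be on day 63 - 10 = 53, outside the period, or the third on day 189 - 10 = 179, inside it. These visits review adverse events and medication but include no pregnancy test. Beyond 28 days, Section 13.1.1 collects only drug-related serious or other clinically significant events, and Section 13.5.1 does not class pregnancy as an SAE.
3. *Survival Follow-up.* Women who stop treatment for progression go straight here (Sections 5.3 and 12.1.4). Contacts are about every 3 months (about 91 days): 120 / 91 = 1.3, so 1 or 2 in the period. They may be by telephone or chart review, and Section 12.1.4 rules out collecting other data "beyond survival will be collected during these calls/visits". Section 5.4 adds only the first subsequent anti-cancer therapy.
4. *The half-life clause in Section 13.5.1.* This concerns pregnancy at the time of exposure, including at least 6 half-lives after dosing, and sets no notification period for the woman. The longest half-life in the protocol is 69 h (total platinum in rats, Table 3). Applying it to humans is an assumption: 6 x 69 = 414 h, and 414 / 24 = about 17 days.

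None of the four clearly closes the gap. Setting the women's window to 180 days after the last dose reduces it to 180 - 180 = 0.

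**The case against.** The case for leaving the text alone has several parts.

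- **The windows need not match.** Contraception is a precaution, whereas Section 13.5.1 ties pregnancy handling to exposure. The components have short half-lives, and 60 days already exceeds the 17 days above. It is true that nothing in the documents requires equal windows. But the protocol makes them equal for men taking the same product and offers no reason to treat women differently.
- **The start of the 180 days is unstated.** This stands, and makes the 120 days conditional. It does not remove the mismatch between the two stated numbers.
- **Other duties have no 60-day limit.** Sites must report any known pregnancy. A birth defect is an SAE (Section 13.2), and related SAEs are reportable without a time limit (Section 13.3.1). These duties narrow the concern, but each depends on the site learning of the event.
- **What women are actually told cannot be seen.** The consent text and the supplements' contraception sections are not available for review. The point is therefore limited to the protocol text for monotherapy.
- **Few women would benefit now.** The SAP reports final enrolment of 110, and its 2022 revision entry refers to study closure. This stands. A change would help only women still within 180 days of a dose, and later studies that reuse the text.

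**Conclusion.** The inconsistency is real. In monotherapy, women are asked to avoid pregnancy for at least 180 days but to report a suspected one for only 60 days after the last dose, while men have 180 days for both. The gap is 120 days if the 180 days run from the last dose, and longer if they run from the end of participation. Pregnancies in days 61-180 may be missed; it does not follow that they will be, because a woman may volunteer the information or it may come up at a visit. The number of women affected cannot be derived from the documents and is likely small. This is a minor point of safety surveillance, worth correcting because the remedy is cheap. It has no bearing on any endpoint, population or statistical result.

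**What to change.** In Protocol Section 13.5, extend the women's notification period from 60 to 180 days after the last dose for monotherapy. For the combination cohorts, tie it to the contraception period in the relevant supplement. In item 15b, and its copy in the synopsis, state that the 180 days run from the last dose, if the clinical team confirms that reading. Align the consent text if it carries the 60-day figure. The half-life wording in Section 13.5.1 can stay, because it addresses exposure and not the woman's duty to notify.

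The cost is one number and one start point, plus consent text only if it repeats the 60 days. No visit or test is added. Because survival contacts do not ask about pregnancy, the instruction has to be given by End of Treatment. The only downside is a few more pregnancy reports to process.
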